4.17.3 Vital Signs

Vital signs data will be listed by subject and visit including the planned time point, and reference ranges based on SS. Flag for a clinically significant assessment will be provided in the listing.

For each scheduled post-baseline visit, descriptive statistics for all vital sign parameters will be presented for absolute values and changes from baseline by treatment group (AZD1402 and placebo) and overall, per each study part. Vital sign shift tables from baseline to maximum on-treatment will be reported. The number of subjects with treatment emergent vital signs abnormalities will summarised considering the following table:

Vital sign		Observed value	Notable change from baseline
Systolic BP (mmHg)	High	≥ 140	Increase of ≥ 20
	Low	< 90	Decrease of ≥ 20
Diastolic BP (mmHg)	High	≥ 90	Increase of ≥ 10
	Low	< 60	Decrease of ≥ 10
Pulse Rate (bpm)	High	≥ 110	Increase of ≥ 20
	Low	< 50	Decrease of ≥ 20
Respiratory Rate (breaths per minute)	High	$> 20/\text{min}$	
	Low	$< 12/\text{min}$	
Temperature (°C)	High	> 37.5	
	Low	< 35	

Abbreviations: BP = blood pressure; bpm = beats per minute.

On-treatment and treatment emergent definition refer all the assessments with an onset date and time on or after the date and time of first dose of IP up to the end of treatment + 96 hours.

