 - (a) Acute coronary syndrome (acute myocardial infarction, unstable angina), coronary intervention with percutaneous coronary intervention / coronary artery bypass surgery or stroke within 6 months.
 - (b) Heart failure NYHA II-IV.
 - (c) Untreated high degree atrioventricular-block ($\geq 3:1$ conduction rate / Grade III block) / significant sinus node dysfunction / pause or therapy requiring tachyarrhythmia.
 - (d) Family history of long QT-syndrome.
 - (e) Hypertrophic cardiomyopathy or clinically significant valvular heart disease.
- 19 Uncontrolled hypertension with BP $> 150/90$ mmHg.
- 20 History of life-threatening asthma attack or asthma attack requiring ventilation.
- 21 **Part 2 only:** History of 3 or more severe asthma exacerbations (defined as a worsening of asthma requiring treatment with systemic corticosteroids for 3 days or more, or hospitalisation/emergency room visit due to asthma) in the 12 months prior to Visit 1.
- 22 Daily rescue use of SABA ≥ 8 puffs for ≥ 3 consecutive days at any time during Run-in Period, before randomisation.
- 23 History of anaphylaxis that required the use of epinephrine or hospitalisation.
- 24 Any clinically significant abnormalities in haematology.
- 25 Alanine aminotransferase or AST level ≥ 3 times the ULN, confirmed by repeated testing during Screening Period. Transient increase of AST/ALT level that resolves by the time of randomisation is acceptable if in the Investigator's opinion, the participant does not have an active liver disease and meets other eligibility criteria.
- 26 History of, or reason to believe a participant has a history of, drug or alcohol abuse within the past 2 years prior to Screening as judged by the Investigator which may include a

positive drugs of abuse test not consistent with the participant's acute or chronic treatment.

27 Planned in-patient surgery, major dental procedure or hospitalisation during the study.

Prior/Concomitant Therapy

28 Systemic corticosteroid use within the 6 weeks before Visit 1, Screening Period and during Run-in.

29 Participants who have previously received AZD1402.

30 Treatment with marketed or investigational biologicals such as monoclonal antibodies or chimeric biomolecules, and within 6 months or 5 half-lives before Visit 1, Screening Period and during Run-in, which includes but is not limited to:

- (a) Anti-IgE (eg, omalizumab).
- (b) Anti-IL5 and anti-IL5R (eg, mepolizumab, reslizumab, benralizumab).
- (c) Anti-IL4R (eg, dupilumab).

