4.17 Safety Evaluation

All safety summaries and analyses will be based upon the SS as defined in Section 4.5.1 and will be presented by dose level of AZD1402, pooled AZD1402, and placebo and by study part.

In general, there will be no imputation of missing data for the safety analyses. All safety data (scheduled and unscheduled) will be presented in the data listings.

Baseline for safety evaluations will be the last value obtained before first study intervention.

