Shift from baseline to maximum and to minimum on-treatment tables will be presented for laboratory parameters (chemistry, haematology and coagulation, urinalysis and immune biomarkers) including all blood white cells. The number of subjects with treatment emergent haematology abnormalities will be summarised.

The criteria for the haematology treatment emergent abnormalities (respect to baseline) are:

- Confirmed leucocyte count $< 2.0 \times 10^9/L$
- Confirmed neutrophil count $< 1.0 \times 10^9/L$
- Confirmed platelet count $< 75 \times 10^9/L$
- Confirmed lymphocyte count $< 0.5 \times 10^9/L$

Shift tables for the immune biomarkers IFNg, IL-10, IL-12p70, IL-13, IL-1b, IL-2, IL-4, IL-6, IL-8, TNFa, CRP, and IgE, will be presented by treatment and separately for each part.

Individual subject data where alanine aminotransferase/transaminase (ALT) and/or aspartate aminotransferase/transaminase (AST) and total bilirubin are elevated at any time will be listed (ie, ALT and/or AST $\geq 3 \times$ the upper limit of normal [ULN] and total bilirubin $\geq 2 \times$ ULN, at any time) to evaluate potential Hy's Law cases.

A figure for both ALT and AST versus total bilirubin expressed as multiple of ULN will be presented. Plot will be produced on the log scale, and reference lines will be included at $2 \times$ ULN for total bilirubin and at $3 \times$ ULN for ALT/AST.

Clinical laboratory data will be reported in the units provided by the clinical laboratory for the SRC meeting (if applicable), and in System International units in the CSR.

The number and percentage of subjects with a change from baseline in hsCRP higher than 5 and 10 mg/dL will be also reported by specified ADA status.

Figure for hsCRP over time by ADA status and by treatment group will be presented.

Statistical Analysis Plan

On-treatment and treatment emergent definition refer all the assessments with an onset date and time on or after the date and time of first dose of IP up to the end of treatment + 96 hours.

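### SAP 4.17.3 defines treatment emergent vital-sign abnormalities by timing alone, so findings already present at baseline can be counted as new

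*SAP*

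**What the plan says.** SAP 4.17.3 (Vital Signs) plans this summary: "The number of subjects with treatment emergent vital signs abnormalities will summarised considering the following table". The table has two criteria columns.

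- The observed-value column gives a high and a low limit for five signs: systolic BP (140 or more, below 90 mmHg), diastolic BP (90 or more, below 60 mmHg), pulse (110 or more, below 50 bpm), respiratory rate (above 20, below 12 per minute) and temperature (above 37.5, below 35 °C).
- The second column, "Notable change from baseline", gives a change of 20 mmHg for systolic BP, 10 mmHg for diastolic BP and 20 bpm for pulse. It is blank for respiratory rate and temperature.

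The section does not say whether both columns must be met, whether either is enough, or whether they are tabulated separately. Its definition of the term is: "On-treatment and treatment emergent definition refer all the assessments with an onset date and time on or after the date and time of first dose", running "up to the end of treatment + 96 hours".

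Three other places bear on this. SAP 4.17 defines the reference value: "Baseline for safety evaluations will be the last value obtained before first study intervention". SAP 4.17.2 heads its blood-count limits differently: "The criteria for the haematology treatment emergent abnormalities (respect to baseline) are". Exclusion 19 in Protocol 5.2 reads "Uncontrolled hypertension with BP" above 150/90 mmHg.

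SAP 4.17.3 also plans change-from-baseline summaries, shift tables from baseline to maximum on-treatment, and listings that flag clinically significant values.

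**The concern.** A timing rule suits adverse events, because an onset date marks something new. A vital-sign reading has only a measurement time, so every reading in the window passes the rule, including one that repeats the pre-dose finding. A participant who breathes 22 times a minute before the first dose and again at Week 2 is then reported as having a treatment emergent abnormality.

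Vital signs are part of the primary safety endpoint in Part 1 and of a secondary safety objective in Part 2 (Protocol Tables 3 and 4). A table that mixes old and new findings raises the count in every arm, placebo included, and brings the arms closer together in relative terms. The missing rule for combining the columns also leaves the programmer to choose, and the choice changes the blood-pressure counts a good deal.

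**Working it through.** The plan states no rate or count for vital-sign abnormalities, so there is no figure to reproduce. The check is of the rule itself, followed by two illustrations on assumed inputs.

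**1. Applying the rule to each sign**

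- Respiratory rate and temperature: the change cells are blank, so the observed value alone decides however the columns combine. Abnormal before dosing and abnormal again in the window is counted.
- Systolic BP: a participant at 145 mmHg before and after dosing passes exclusion 19 and meets the limit of 140. The change is 0, below 20. The participant is counted if the observed value alone, or either column, is enough, and is not counted if both are required.
- Diastolic BP: the exclusion is above 90 and the high limit is 90 or more, so the overlap at the eligibility reading is the single value 90.
- Pulse and the low limits: the eligibility criteria set no numeric bound on pulse, respiratory rate, temperature or low blood pressure.
- Low values: vital-sign shift tables go to the maximum only, whereas the laboratory shift tables in SAP 4.17.2 go to maximum and minimum.

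**2. How much the column rule matters for systolic BP**

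This is a simulation with no drug effect. All inputs are assumed: true level normal with mean 122, 126 or 130 mmHg and between-person SD 10, 11 or 12 respectively; within-person SD 8; entry if the screening reading is 150 or less; one baseline reading and four post-dose readings (Visits 4 to 7 in Part 2).

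| Mean level (mmHg) | 122 | 126 | 130 |
|---|---|---|---|
| Baseline 140 or more | 7.8% | 14.0% | 20.9% |
| Counted, observed value only | 19.9% | 31.2% | 41.8% |
| Counted, either column | 27.8% | 37.4% | 46.8% |
| Counted, both columns | 4.6% | 6.2% | 7.5% |
| Newly 140 or more (share of all participants) | 14.5% | 20.4% | 24.3% |
| Of those high at baseline: counted, observed only or either | 67.9% | 77.2% | 83.7% |
| Of those high at baseline: counted, both | 0.7% | 1.3% | 2.0% |

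On the observed-only reading, the pre-existing share of the counted cases is (19.9 − 14.5)/19.9 = 27%, (31.2 − 20.4)/31.2 = 35% and (41.8 − 24.3)/41.8 = 42%.

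**3. Effect on a contrast between arms**

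Let b be the share abnormal at baseline, r the share of those who are abnormal again in the window, and p the true new-onset rate among the rest. Then

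counted rate = r·b + (1 − b)·p.

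With r = 1 and assumed p of 5% (placebo) and 10% (active):

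- b = 10%: 0.10 + 0.90 × 0.05 = 14.5% and 0.10 + 0.90 × 0.10 = 19.0%; ratio 1.31, difference 4.5 points
- b = 20%: 24.0% and 28.0%; ratio 1.17, difference 4.0 points
- b = 30%: 33.5% and 37.0%; ratio 1.10, difference 3.5 points

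Counting new onset only, among those normal at baseline, gives 5% and 10%: ratio 2.0, difference 5 points. If b and r are the same in both arms, the difference is (1 − b)(p₁ − p₀) whatever r is. The ratio is diluted much more than the difference.

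**The case against.** The strongest reply is that the table carries its own baseline reference. If both columns must be met, a stable 145 mmHg is not counted, and the simulation then counts at most 2% of those who start high. The haematology section supports this reading to a degree: it ends with the same timing sentence yet states its criteria relative to baseline, so the sentence may set only the window and leave room for a separate baseline condition. This stands for blood pressure and pulse, where the fault is an unstated rule. It does not help respiratory rate or temperature, which have no change criterion and no baseline wording.

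The second reply is that other outputs hold the information. Shift tables to maximum separate old from new high values, change summaries and listings are planned, clinically relevant deterioration is reported as an adverse event (Protocol 8.3.6), and confirmed fever is an adverse event of special interest. This largely stands for high values. It does not give a table that separates baseline-low from newly low.

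A reader might infer that every eligible participant with raised blood pressure will be reported as an emergent case at any time after first dose. The documents do not support that: the column rule is open, the window closes 96 hours after treatment ends, and the diastolic overlap with eligibility is one value.

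**Conclusion.** The point holds as a labelling fault in one descriptive safety table. It is definite for respiratory rate and temperature. For blood pressure and pulse it depends on a combining rule that the SAP does not state. The gap for low values is also definite.

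Its size cannot be derived from the documents, which give neither baseline nor new-onset rates. The ratios of 1.31 to 1.10 in place of 2.0 rest on assumed rates, on every baseline-abnormal participant recurring, and on equal baseline shares across arms. The absolute difference would fall only from 5 points to between 4.5 and 3.5. A reader might conclude from the ratios that a real safety difference would be hidden. That is not supported, because no vital-sign hypothesis is tested and the other planned outputs remain available. The priority is low, but the change is cheap.

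**What to change.** In SAP 4.17.3:

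- Count an abnormality as treatment emergent only if the observed-value criterion is met in the window and was not met at the last pre-dose value. Use as denominator the participants who did not meet that criterion at baseline, and show that number. Apply this to all five vital signs, high and low.
- Tabulate the notable-change criterion separately, for all participants. This removes the question of how the columns combine and still shows worsening from an already abnormal blood pressure or pulse.
- Add shift tables from baseline to minimum on-treatment.

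The cost is a sentence or two, one programming condition and one further set of shift tables. SAP section 1 provides for such a change through a new version before database lock. The downside is that an individual's worsening from an already abnormal respiratory rate or temperature would leave this table. It would be seen only in the listings and, as far as their categories allow, in the shift tables.

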4.17.4 Electrocardiogram

Standard safety 12-lead ECGs will be performed as shown in the SoA.

The following ECG parameters will be recorded:

- QRS interval (msec)
- RR-interval (msec)
- PR-interval (msec)
- QT interval (msec)
- QT-interval corrected using the Bazett correction formula (QTcB) (msec)
- QT-interval corrected using the Fridericia correction formula (QTcF) (msec)
- Heart rate (HR) (bpm)

The ECG will be evaluated by the investigator as 'Normal', 'Abnormal' or 'Borderline' and will be tabulated at baseline versus last value on-treatment by each dose and each part.

All ECG parameters will be listed by subject for each dose cohort and time point and each part. The baseline for the ECG measurements will be obtained pre-dose on Day 1.

Descriptive statistics (n, mean, SD, median, minimum, maximum) over time for absolute values and changes from baseline will be presented by each dose cohort and each Part. Categorical QT and QTc analyses will also be performed.

Shift tables will report the shift from baseline to the maximum value on-treatment: the number and percentage of subjects with QT/QTc intervals exceeding some predefined upper limits (eg, > 450 msec, > 480 msec, > 500 msec for absolute values as well as > 30 msec, > 60 msec for increase from baseline) of ECG parameters.

Abnormalities in electrocardiogram data will be listed based on SS.

On-treatment definition refer all the assessments with an onset date and time on or after the date and time of first dose of IP up to the end of treatment + 96 hours.

4.17.5 Spirometry

In-clinic and home spirometry values (FEV₁ and FVC) will be listed by subject and timepoint including absolute values, change from baseline, and percentage change from baseline.

Change from baseline will be calculated and presented by timepoint in each study part. Summary tabulations for absolute values, change from baseline and percentage change from baseline will be presented by treatment group (AZD1402, pooled AZD1402, and placebo) and overall, and by timepoint for in-clinic and e-Diary spirometry FEV₁. For in-clinic FVC similar tables will be presented.

For repeated post-baseline in-clinic spirometry morning measurements that are taken on the same day and time as a scheduled visit and timepoint, the best response value of the morning pre-dose will be used.

For repeated post-baseline home spirometry measurements that are taken on the same day and time as a scheduled visit and time point, the highest results of the morning pre-dose will be used.

For repeated follow-up post-baseline in-clinic spirometry morning measurements that are taken on the same day and time as a scheduled visit and time point, the best response value of the morning assessments will be used.

For repeated follow-up post-baseline home spirometry measurements that are taken on the same day and time as a scheduled visit and time point, the highest results of the morning assessments will be used.

For Part 1, tables and figures presenting FEV₁ by study day will be based on the morning pre-dose values in case not differently indicated.

For Part 1 and/or Part 2 the following figures will be presented:

- In-clinic FEV₁ absolute values (L), individual subject by study day/week.

Statistical Analysis Plan

- In-clinic FEV₁ percentage change from baseline, individual subject data by study day/week.
- FEV₁ home spirometry absolute values (L), individual subject data by study day.
- FEV₁ home spirometry percentage change from baseline, individual subject data by study day.
- In-clinic FEV₁ mean absolute values (L) by study day/week and treatment group.
- In-clinic FEV₁ mean percentage change from baseline by study day/week and treatment group.
- FEV₁ home spirometry mean absolute values (L) by study day and treatment group.
- FEV₁ home spirometry mean percentage change from baseline by study day and treatment group.

The summary statistics for FEV₁ in-clinic spirometry and e-Diary spirometry will be presented separately.

For in-clinic FEV₁ for Part 1, the morning and evening post-dose percentage change from pre-dose by day, will also be summarised.

4.17.6 Fractional Exhaled Nitric Oxide

Fractional exhaled nitric oxide will be listed by subject and timepoint including the date/time of the assessment, percentage changes from baseline and repeat/unscheduled measurements.

Descriptive statistics (n, mean, SD, median, minimum, maximum) for absolute values and percentage changes from baseline will be presented by treatment group (AZD1402 and placebo) and by pooled AZD1402 groups.

4.18 Data Monitoring Committees

The SRC including the Sponsor study team will review PK and unblinded safety data following completion of Part 1a before progressing to Part 1b/2 and following completion of Part 1b. An unscheduled SRC meeting may also be held in the event of any safety or tolerability events requiring further review that may impact continuation of a cohort or the study, including unblinding data as required. All details on how the safety reviews are conducted are described in the SRC charter. A DSMB will oversee Part 2 of the study and review the unblinded interim outputs. In addition to a full DSMB periodic review of safety data, the committee can meet on an ad hoc basis. Details of the composition of the DSMB, frequency of meetings and remit can be found in the DSMB Charter. A separate review committee of AstraZeneca representatives will review the unblinded interim outputs for the interim analysis if performed.

4.19 Determination of Sample Size

In Part 1 (lead-in cohort), approximately 45 participants will be randomised. Part 1a will consist of 30 randomised participants and Part 1b will consist of 15 randomised participants. The sample size for Part 1 (lead-in cohort) is not based on any sample size calculation but was chosen to obtain reasonable evidence of safety and tolerability without exposing undue number of participants to the study intervention. In Part 2 (main cohort), 73 evaluable participants per treatment arm (████ mg and placebo) will provide █████% power using a 1-sided test and 5% significance level to detect a difference of 175 mL in FEV₁ between AZD1402 versus placebo. This is based on a SD of █████ mL, derived from an inter-participant SD of █████ mL in change from baseline to Week 4, adjusted for 4 repeated measurements and a correlation of █████ between weekly measurements. Assuming a dropout rate of

Statistical Analysis Plan

█████%, approximately 80 evaluable participants per arm are needed. Due to the restricted recruitment into the █████mg dose arm the precision of inference in terms of statistical power will be less than █████% for the comparisons █████mg versus placebo. A participant will be considered evaluable if he/she has a baseline and Week 4 FEV₁ results available. Part 2 will consist of approximately 165 participants.

4.20 Change in the Conduct of the Study or Planned Analysis

SAP updated for anticipated closure to remove some of the exploratory endpoints, the Per Protocol analysis and subgroup analysis.

5 APPENDICES

5.1 Schedule of Assessments

Table 2 Schedule of Activities Part 1

Procedure	Screening	Run-in	Treatment Period ^a								ETV/ IPD	Follow-up		Details in CSP Section or Appendix	
Visit	1	2	3				4,5,6	7		8	9		10	11	
Day	(up to 14 days before V2) ^{b,c}	-28 ± 2	-1	1	2 to 13	14	16, 20, 24	28 ^d - 2	29	30	32		39 ± 6	56 ± 4	
Signed informed consent	X														5.1
Admission			X					X							4.1.1
Discharge						X ^e			X						4.1.1
Optional residential stay (throughout Treatment Period)							X								4.1.1
Inclusion and exclusion criteria	X	X	X	X											5.1, 5.2
Demography	X														5.1
Medical/surgical history	X														5.1
Smoking history including cotinine testing	X							X							5.1
Asthma history	X														5.1
Concomitant medication	X	X	X	X	X	X	X	X	X	X	X	X	X	X	6.5
Height/weight ^f	X							X					X		8.2.1

Table 2 Schedule of Activities Part 1

Procedure	Screening	Run-in	Treatment Period ^a								ETV/ IPD	Follow-up		Details in CSP Section or Appendix
Visit	1	2	3		4,5,6	7		8	9		10	11		
Day	(up to 14 days before V2) ^{b,c}	-28 ± 2	-1	1	2 to 13	14	16, 20, 24	28 ^d - 2	29	30	32		39 ± 6	56 ± 4
Physical examination	X ^g			X ^h					X ^h			X ^g	X ^h	X ^g
Vital signs (blood pressure, pulse rate, temperature, respiratory rate) ⁱ	X	X	X	X	X	X	X	X	X	X	X	X	X	8.2.2
Study drug inhalation training		X	X	X ^j										6.1.3
Home device dispensation (FeNO and spirometer)		X												6.1.2
Home device training (FeNO and spirometer)		X		X ^j										6.1.2
Rescue medication (eg, salbutamol) ^k	X	X	X	X	X	X	X	X	X	X	X	X	X	6.5.1
FeNO test (in-clinic) ^l	X	X	X	X	X	X	X	X	X	X	X	X	X	8.1.3
FeNO at-home assessments (Niox Vero) ^{l, m}		X				X	X			X	X	X	X	8.1.3

Table 2 Schedule of Activities Part 1

Procedure	Screening	Run-in	Treatment Period ^a								ETV/ IPD	Follow-up		Details in CSP Section or Appendix	
Visit	1	2	3		4,5,6	7		8	9		10	11			
Day	(up to 14 days before V2) ^{b,c}	-28 ± 2	-1	1	2 to 13	14	16, 20, 24	28 ^d - 2	29	30	32		39 ± 6	56 ± 4	
Spirometry (FEV ₁ and FVC) ⁿ	X	X	X	X	X	X	X	X	X	X	X	X	X	X	8.1.1
12-lead ECG ^o	X			X	X (Day 7)	X		X							8.2.3
ACQ-6	X	X		X	X (Day 7)	X	X(Day 20)	X				X			8.1.10
FEV ₁ /PEF (home device) ^p		X	X	X	X	X	X	X	X	X	X	X	X	X	8.1.1, 8.1.11
Cough VAS		X	X	X	X	X	X	X	X	X	X	X	X	X	8.1.10
SPFQ (optional)		X				X						X		X	8.1.10
Assign e-Diary ^q	X														8.1.4
Dispense e-Diary ^r		X													8.1.4

Table 2 Schedule of Activities Part 1

Procedure	Screening	Run-in	Treatment Period ^a								ETV/ IPD	Follow-up		Details in CSP Section or Appendix
Visit	1	2	3		4,5,6	7		8	9		10	11		
Day	(up to 14 days before V2) ^{b,c}	-28 ± 2	-1	1	2 to 13	14	16, 20, 24	28 ^d - 2	29	30	32		39 ± 6	56 ± 4
Check e-Diary compliance			X	X	X	X	X	X	X	X	X	X	X	6.4.2
Check compliance with background medication			X	X	X	X	X	X	X	X	X	X	X	6.5
Collect e-Diary												X	X	8.1.4
Asthma symptom score and rescue medication use		X	X	X	X	X	X	X	X	X	X	X	X	8.1.6, 8.1.7
Study drug dispensation						X								6.1
Study drug administration ^s	CCI													6.1.3
Drug accountability								X				X		6.2
Return unused medication and DPI								X				X		6.2
AEs ^t	X	X	X	X	X	X	X	X	X	X	X	X	X	8.3
Blood samples for biochemistry	X	X		X ^u	X ^v	X	X	X		X		X	X	8.2.4
Blood samples for haematology	X	X		X ^u	X ^v	X	X	X		X		X	X	8.2.4
Blood samples for clotting profile	X	X		X ^u	X ^v	X	X	X		X		X	X	8.2.4
Blood samples for CRP (local laboratory) ^w			X	X	X	X	X	X	X	X	X	X	X	8.2.4
Blood sample for hs-CRP	X	X		X ^u	X ^v	X	X	X		X		X	X	8.2.5.1

Table 2 Schedule of Activities Part 1

Procedure	Screening	Run-in	Treatment Period ^a								ETV/ IPD	Follow-up		Details in CSP Section or Appendix	
Visit	1	2	3				4,5,6	7		8	9		10	11	
Day	(up to 14 days before V2) ^{b,c}	-28 ± 2	-1	1	2 to 13	14	16, 20, 24	28 ^d - 2	29	30	32		39 ± 6	56 ± 4	
Blood samples for safety immuno-biomarkers	X	X		X ^u	X ^v	X	X	X		X		X	X	X	8.2.4
Blood samples allergen-specific IgE ^x			X												8.6.1
Blood samples for serum pregnancy test (all female participants)	X														5.1, 8.2.4
Blood samples for Hepatitis B (HBsAg, anti-HBs, anti-HBC), and C; HIV-1 and HIV-2; QFT for TB ^y	X														5.1, 8.2.4
Blood samples for PK measurements ^z				X	X	X	X	X	X	X	X	X	X	X	8.5.1
Blood samples for ADA ^{aa}				X		X	X (Day 20, 24)	X			X	X	X	X	8.5.2
CCI bb				X											8.6.2, 8.7
CCI bb				X (pre-dose)				X (pre-dose)			X		X	X	8.6.2
Urinalysis	X	X		X ^u	X ^v	X	X	X		X		X	X	X	8.2.4

Table 2 Schedule of Activities Part 1

Procedure	Screening	Run-in	Treatment Period ^a								ETV/ IPD	Follow-up		Details in CSP Section or Appendix	
Visit	1	2	3				4,5,6	7		8	9		10	11	
Day	(up to 14 days before V2) ^{b,c}	-28 ± 2	-1	1	2 to 13	14	16, 20, 24	28 ^d - 2	29	30	32		39 ± 6	56 ± 4	
Blood samples for FSH (if needed to confirm postmenopausal status in female participants < 50 years and not on HRT)	X														5.1, 8.2.4
Urine pregnancy test (females of childbearing potential) ^{cc}			X					X				X		X	5.1, 8.2.4
Urine drug screen	X							X							5.2, 8.2.4
SARS-CoV-2 PCR ^{dd}	X	X	X ^{ee}	X	X	X	X	X	X	X	X	X	X	X	5.2, 8.2.4
SARS-CoV-2 serology ^{dd}	X											X		X	5.2, 8.2.4

Abbreviations: ACQ-6 = Asthma Control Questionnaire-6; ADA = anti-drug antibody; AE = adverse event; AESI = adverse event of special interest; CCI [REDACTED] COVID-19 = Coronavirus disease-2019; CRP = C-reactive protein; CSP = clinical study protocol; DPI = dry powder inhaler; ECG = electrocardiogram; e-Diary = electronic diary; ETV = early termination visit; FEV₁ = forced expiratory volume in 1 second; FeNO = fractional exhaled nitric oxide; FSH = follicle stimulating hormone; FVC = forced vital capacity; CCI [REDACTED] HBsAg = hepatitis B surface antigen; HIV = human immunodeficiency virus; CCI [REDACTED] HRT = hormone replacement therapy; hs-CRP = high sensitivity CRP; IgE = immunoglobulin E; IPD = Intervention Discontinuation Visit; CCI [REDACTED] PCR = polymerase chain reaction; PEF = peak expiratory flow; PK = pharmacokinetics; QFT = QuantiFERON; SARS-CoV-2 = severe acute respiratory syndrome coronavirus 2; SPFQ = Study Participant Feedback Questionnaire; SoA = Schedule of Activities; TB = tuberculosis; VAS = Visual Analogue Scale

^a In-clinic outpatient visits during the Treatment Period will be scheduled so that they fall at the time of morning dose administration.

^b Time between Visit 1 and Visit 2 may be extended up to 28 days upon input from the Study Physician.

^c Visit 1 can be done on several/different days prior to Visit 2.

^d Participants may be admitted on Day 27. Day 28 should be performed on the scheduled calendar day as far as possible; the -2-day window may be utilised only if required. If the -2-day window is utilised, all subsequent visits will be adjusted to follow time window between visits as specified in the SoA.

^e Discharge on Day 14 after the morning post-dose procedures.

f Height only at Visit 1.

g A complete physical examination including an assessment of the general appearance, respiratory, cardiovascular, abdomen, skin, head and neck (including ears, eyes, nose and throat), lymph nodes, thyroid, musculoskeletal and neurological systems will be performed.

h A brief physical examination including an assessment of the general appearance, skin, abdomen, cardiovascular, and respiratory systems will be performed.

i Vital signs to be performed BID whilst participants are in-clinic. Vital signs will be measured pre-dose at the scheduled morning dose in-clinic visits and additionally prior to the evening dose if participants receive the evening dose at the clinic (eg, due to optional overnight stay).

j Refresher training as required.

k Rescue medication to be as necessary. Check if participant has enough rescue medicine for use at-home use and refill if necessary.

l FeNO will be measured pre-spirometry, pre-dose (as applicable), and pre-bronchodilation.

m FeNO assessments at home will only be performed (morning and evening) at non-clinic visit timepoints.

n In-clinic spirometry on Days 1 to 14 and Day 28 will be performed pre-dose and 2 h post-dose (\pm 15 min) in the morning (prior to taking controller medication) and on Days 1 to 13 pre-dose and 4 h post-dose (-2 h) in the evening. Where possible, all post-randomisation morning pre-dose clinic spirometry assessments should be performed within \pm 30 minutes of the time that the randomisation spirometry was performed during the residential period. The evening pre-dose spirometry should also be performed within a \pm 30 minutes window relative to the evening assessment timepoint. If patients remain in the unit without discharge to stay overnight during Days 14 to 27, a pre-dose and 2 h post-dose spirometry assessment will be performed in the morning (prior to taking controller medication) and pre-dose and 4 h (-2h) post-dose spirometry assessment in the evening. If patients are discharged and re-admitted to the unit for overnight stay on Days 15 to 27, the morning and evening post-dose spirometry assessment will be 4 h (-2h) post-dose (controller medication timing will remain unchanged from home dosing and controller medication will be taken directly after study intervention). At clinic visits with no overnight stay, morning pre-bronchodilator and 2 h post spirometry will be performed. The timing of controller medication and clinic post-dose spirometry assessments may be adjusted by the Sponsor.

o ECG will be measured before (within 75 min) and 1 hour (\pm 10 min) after administration of study intervention on visits as indicated.

p Home device spirometry will be performed pre-dose twice daily, including on in-clinic assessment days. On in-clinic assessment days, home spirometry may be performed up to 2 hours prior to dosing.

q At Visit 1 the e-Diary is set up, participants perform training and ACQ-6 and SNOT-22 is completed.

r The e-Diary will be completed twice daily during the Run-in, Treatment, and Follow-up Period.

s Study intervention will be administered **CCI** While at clinic, the study drug administration will be monitored by the site staff. Administration will be registered in the e-Diary by the participant.

t AEs will be collected from the time of informed consent. Unscheduled safety sampling may be performed at the discretion of the Investigator in the event of AEs/AESIs, including but not limited nasal swabs to confirm infection.

u Baseline safety sampling will be performed pre-dose on Day 1.

v Sampling on Days 2, 6, 8, 10, and 12.

w CRP must be done locally on Day -1 (may be performed on Day -2 for logistical reasons) to confirm eligibility as per inclusion criterion. It may be performed throughout the study in the event of AE/AESI as required to inform suspension/stopping criteria.

x Blood samples will be analysed for IgE if potential drug related IgE response is observed in any participant; may be collected on Day -1 or Day 1 pre-dose.

y PCR may be performed to confirm hepatitis B / hepatitis C status if required.

^z Blood samples for PK measurements will be collected for all participants. Timing of samples: Day 1 pre-dose (-60 min), 1, 2, 3 (\pm 10 min), 4, 6, 8 (\pm 20 min) and 12 h (up to 1h prior to the next dose, must be before the subsequent dose); Day 28 pre-dose (-60 min), 1, 2, 3 (\pm 10 min), 4, 6, 8 (\pm 20 min), and 12h (\pm 1 h; single dose of AZD1402 only on Day 28). Pre-dose on Days 2, 4, 6, 8, 10, 12, 14, 16, 20, 24 (up to 1 h prior to the next dose, must be before the subsequent dose), 29 (24 h \pm 2 h after Day 28 dose), 30 (48 h \pm 2.5 h after Day 28 dose), 32 (96 h \pm 2.5 h after Day 28 dose), 39 (\pm 6 days), and 56 (\pm 4 days). Part Ib only: Day 20, 4 h post-morning dose (\pm 20 min). The PK sampling timepoints may be amended based on results from Part 1a/b. An unscheduled PK sample may be collected in the case of AEs and / or unscheduled safety blood sampling.

^{aa} ADA sampling, pre-dose Day 1, Day 14, Day 20, Day 24 (Part 1b only) and Day 28 and on Follow-up/unscheduled visits. Participants **CCI** [REDACTED] An unscheduled ADA sample may also be collected in case of AEs/AESIs and/or unscheduled safety blood sampling.

^{bb} Sample collection if consented only. If for any reason the sample is not drawn at Visit 3, it may be taken at any visit until the last study visit.

^{cc} All urine pregnancy tests will be done pre-dose.

^{dd} SARS-CoV-2 serology at Screening, End of Trial and final Follow-up Visits; PCR is optional and may be performed centrally or at the local laboratory as clinically indicated and as per local guidelines for the duration of the study. Ad hoc nasal and/or throat-swab specimen is to be collected for the identification of a suspected respiratory infection during any visit. This may be performed locally, or if required by central laboratory.

^{ee} May be performed on Day -2 for logistical reasons.

Table 3 Schedule of Activities Part 2

Procedure	Screening	Run-in	Treatment Period ^a					ETV/ IPD	Follow-up		Unscheduled Visit	Details in CSP Section or Appendix
Visit	1	2	3	4	5	6	7		8	9		
Day	(up to 14 days before V2) ^{b,c}	-28 ± 2	1	7 ± 2	14 ± 2	21 ± 2	28 ± 2		39 ± 6	56 ± 4		
Week	-6	-4	0	1	2	3	4		5/6	8		
Signed informed consent	X											5.1
Inclusion and exclusion criteria	X	X	X									5.1, 5.2
Demography	X											5.1
Medical/surgical history	X											5.1
Smoking history including cotinine testing	X											5.1
Asthma history	X											5.1
Concomitant medication	X	X	X	X	X	X	X	X	X	X		6.5
Height/weight ^d	X						X					8.2.1
Physical examination	X ^e		X ^f				X ^f	X ^f	X ^f			8.2.1
Vital signs (blood pressure, pulse rate, temperature, respiratory rate) ^g	X	X	X	X	X	X	X	X	X	X		8.2.2
Study drug inhalation training		X	X ^h									6.1.3
Home device (spirometer) dispensation		X										6.1.2
Home device training (spirometer)		X	X ^h									6.1.2

Procedure	Screening	Run-in	Treatment Period ^a					ETV/ IPD	Follow-up		Unscheduled Visit	Details in CSP Section or Appendix
Visit	1	2	3	4	5	6	7		8	9		
Day	(up to 14 days before V2)^{b,c}	-28 ± 2	1	7 ± 2	14 ± 2	21 ± 2	28 ± 2		39 ± 6	56 ± 4		
Week	-6	-4	0	1	2	3	4		5/6	8		
Rescue medication (eg, salbutamol) ⁱ	X	X	X	X	X	X	X	X	X	X		6.5.1
FeNO test (in-clinic) ^j	X	X	X	X	X	X	X	X	X		X	8.1.3
Spirometry (FEV ₁ and FVC) ^k	X	X	X	X	X	X	X	X	X		X	8.1.1
Reversibility test ^l	X											8.1.2
12-lead ECG ^m	X		X				X					8.2.3
ACQ-6	X	X	X	X	X	X	X	X	X			8.1.10
SPFQ (optional)			X		X			X		X ⁿ		8.1.10
FEV ₁ /PEF (home device) ^o			X	X	X	X	X		X			8.1.1, 8.1.11
Assign e-Diary ^p	X											8.1.4
Dispense e-Diary ^q		X										8.1.4
Check e-Diary compliance			X	X	X	X	X	X	X	X	X	6.4
Check compliance with background medication			X	X	X	X	X	X	X	X	X	8.1.4
Check compliance with study medication			X	X	X	X	X				X	
Collect e-Diary								X		X		8.1.5
Asthma symptom score and rescue use		X	X	X	X	X	X	X	X			8.1.6, 8.1.7
Study drug dispensation			X		X							6.1

Procedure	Screening	Run-in	Treatment Period ^a					ETV/ IPD	Follow-up		Unscheduled Visit	Details in CSP Section or Appendix
Visit	1	2	3	4	5	6	7		8	9		
Day	(up to 14 days before V2) ^{b,c}	-28 ± 2	1 ± 2	7 ± 2	14 ± 2	21 ± 2	28 ± 2		39 ± 6	56 ± 4		
Week	-6	-4	0	1	2	3	4		5/6	8		
Study drug administration ^r	CCI											6.1
Drug accountability					X			X	X			6.2
Return unused medication and inhaler					X			X	X			6.2
AE ^s	X	X	X	X	X	X	X	X	X	X		8.3
Blood samples for biochemistry	X		X ^t		X	X	X	X	X		X	8.2.4
Blood samples for haematology	X	X	X ^t		X	X	X	X	X		X	8.2.4
Blood samples for clotting profile	X											8.2.4
Blood sample for hs-CRP	X	X	X ^t		X	X	X	X	X		X	8.6.1
Blood samples for safety immuno-biomarkers	X		X ^t		X	X	X	X	X		X	8.2.5.1
Blood samples allergen-specific IgE ^u			X ^u									8.2.4
Blood samples for CRP (local laboratory) ^v			X	X	X	X	X	X	X	X		8.2.4
Blood samples for serum pregnancy test (all female participants)	X											5.1, 8.2.4
Blood samples for Hepatitis B (HBsAg, anti-HBs, anti-HBc), and C; HIV-1 and HIV-2; QFT for TB ^w	X											5.1, 8.2.4
Blood samples for PK measurements ^x			X		X	X	X	X	X		X	8.5.1
Blood samples for ADA ^y			X		X	X	X	X	X	X		8.5.1

Procedure	Screening	Run-in	Treatment Period ^a					ETV/ IPD	Follow-up		Unscheduled Visit	Details in CSP Section or Appendix
Visit	1	2	3	4	5	6	7		8	9		
Day	(up to 14 days before V2) ^{b,c}	-28 ± 2	1 ± 2	7 ± 2	14 ± 2	21 ± 2	28 ± 2		39 ± 6	56 ± 4		
Week	-6	-4	0	1	2	3	4		5/6	8		
CCI [REDACTED] z			X									8.6.2, 8.7
CCI [REDACTED]			X aa		X aa		X aa	X	X aa			8.6.1
CCI [REDACTED]			X aa				X aa	X	X aa			8.6.1
CCI [REDACTED]			X aa									
Urinalysis	X											8.2.4
Blood samples for FSH (if needed to confirm postmenopausal status in female participants < 50 years and not on HRT)	X											5.1, 8.2.4
Urine pregnancy test (females of childbearing potential) ^{bb}			X				X	X		X		5.1, 8.2.4
Urine drug screen	X											5.2, 8.2.4
SARS-CoV-2 PCR ^{cc}	X	X	X	X	X	X	X	X	X	X		5.2, 8.2.4
SARS-CoV-2 serology ^{cc}	X											5.2, 8.2.4

